Alternative study timeline: Due to funding constraints, participants enrolled February 2018 or after will be involved in study-related activities for about 4 months (18 weeks) from initial enrollment in the observational study and baseline assessment (week -4) through a final follow-up at week 14. Participants enrolled in this alternative study timeline will complete three phone-based assessments (Baseline/Week -4; Week 6; Week 14) and those who report abstinence from cigarettes at the Week 14 phone interview will be invited to come in for an in-person clinic visit within 2 weeks of their Week 14 phone session in order to bioverify smoking status. Randomization to treatment arm and all other study procedures will be conducted in the same way as for the participants completing the full 32 week study timeline.

Study Timeline

Development of Bilateral EHR Interface with the Quitline. Led by Drs. [name] and [name], we will complete the testing and refinement of the bilateral EHR interface between NNHSC and the Quitline. Trainings with providers in use of the new EHR functionality will also be conducted. The integration of NNHSC and the Quitline will enable the NNHSC study care coordinator and providers to make a one-step referral to the Quitline. In turn, the Quitline will communicate patient outcomes directly to NNHSC via the EHR. The existing EHR content will be modified to automate obtaining and documenting provider approval of patient involvement and generating and documenting the mailing of the intervention letters. All clinical information will be communicated to the Quitline using Health Level Seven (HL7) standards. The Quitline will use a HL7 interface engine to receive and “translate” the information within its secure network.

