Retention and Adherence

Based upon our past experience with clinical trial and prospective cohort studies of diverse populations (R01 DA025078; N01 HC48049), we expect at least a 60% participation rate across the four surveys. In our recent smoking cessation trial,⁹⁴ of the 1,989 sessions scheduled for the 259 participants at the Northwestern clinical site over their first 6 months, 1,604 (81%) were completed.

To maximize enrollment in this study, we will:

- 1) Target patients who are most likely to view one of the NNHSC clinical sites as their medical home through defining eligibility based in part on at least one clinic visit during the past year;¹⁰⁷
- 2) Include monetary compensation for each survey completion, plus \$50 for completing the in-person session at week 28 (original timeline) or week 14 (alternative shorter timeline);¹⁰⁷ and
- 3) Develop and implement strategies to engage the NNHSC community.^{108,109} Drs. [name] and [name], along with [name], will provide critical guidance on best practices and issues of cultural competency related to research targeting low-income and African American populations.^{110,111} For example, we plan to conduct a clinic-wide outreach campaign across the seven participating NNHC clinics to increase interest in the health habits survey. Additionally, we will use small, low-cost giveaways to increase recognition of the survey once research assistants because to recruit and enroll patients.

We have developed a plan to maximize retention of participants to overcome follow-up challenges that are often experienced in longitudinal studies of low-income populations,¹¹²⁻¹¹⁴ such as residential instability. Strategies will include the following:

- 1) A user-friendly electronic tracking database of participants;
- 2) Elicitation at baseline and every follow-up session of relative and (or) neighbor contacts to locate participants if needed;
- 3) Research personnel training on team building and positive attitudes;
- 4) Flexible scheduling of telephone sessions, including Saturday appointments;
- 5) Sending personalized reminder cards and retention items (i.e., water bottles, draw string bags, earbuds, T-shirts);
- 6) Reminder letters with small giveaway items sent one week prior to their scheduled session and reminder calls to participants 1-2 days prior to their scheduled session
- 7) Establishing strong rapport with participants by providing a friendly experience during assessments;

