All outcomes of interest for **Primary Aims 1-3** are binary (treatment engagement, treatment utilization, smoking cessation) and can be analyzed using logistic regression methods. Analyses will be conducted first using an ITT principle (missing=treatment failures). We will also conduct an adherence sample analysis that includes only participants reached at the 28-week follow-up ($\geq 75\%$ of the sample based on our experience). This approach addresses the question of effectiveness more directly, but it is subject to more bias if attrition is large or differential by treatment condition. Therefore, we will complement it by analysis of non-response patterns using sociodemographic (age, gender, race, ethnicity, marital status, household income, education), and healthcare (time since last clinic visit, type of health insurance) characteristics. These can be used to create propensity scores that allow for inverse-probability-weighting (IPW) of observed outcomes^{116,117} to achieve balance across potential confounders of the treatment-to-outcome relationship. Ideally, the distribution of propensity scores will show large overlap across study conditions. If not, that will be taken as evidence that completers are not comparable on measured confounders across conditions, and that one should refrain from

PROTOCOL SHORT TITLE: Choose to Change – Reducing Tobacco Disparities

further comparisons. PROC GENMOD of SAS/STAT 9.2¹¹⁸ can handle subject-level probability weights. Similar findings across all three approaches would increase confidence in the results overall. Both raw and adjusted rates will be presented for each outcome by study condition. For the cessation outcome, we will also explore the impact of smoking history (e.g., past year quit attempts, past referral for Quitline treatment), race, and gender on non-response. We will also use propensity score modeling to examine the relationship between treatment utilization at 14 weeks and abstinence at 28 weeks. Since available data indicate little effect of NRT type on outcome, we will model NRT dose/duration, while controlling for patterns of utilization.

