[name] (UIC Co-PI) and [name] (UIC Co-I) contribute their expertise in community-based participatory research in smoking cessation among low-income and disenfranchised populations, and [name], specifically, designed our recruitment and retention plan. [name] (NEIU Co-PI) will be leading the cost evaluation component of the study.

Alliance of Chicago will provide research and EHR technical expertise for NNHSC's EHR (i.e., Alliance will build the e-Referral, e-Outcomes and letter components of the Choose to Change intervention within NNHSC's EHR.

PROTOCOL SHORT TITLE: Choose to Change – Reducing Tobacco Disparities

The Illinois Tobacco Quitline will provide their evidence-based cessation treatment to all participants who accept the referral and proactive call from the Quitline counselors. The Quitline staff will conduct the same counseling to study participants that they do to any other caller or patient referred for services. They will also electronically send the treatment outcomes information to the NNHSC EHR for all participants who complete Quitline counseling sessions.

All partners, academic and community-based, will be provided with a current IRB-approved protocol. As all staff conducting the research activities are NU staff, we hold regular weekly meetings to ensure successful coordination of these activities and ongoing research protocol monitoring.

Community-Based Participatory Research

The Choose to Change intervention has benefitted from six-year collaboration with NNHSC, including Winfield Moody Health Center, Alliance, and the Illinois Tobacco Quitline. NNHSC providers and patients guided and contributed to the development of key aspects of the Choose to Change intervention, including the letter, and clinical workflow. Because of this long-term partnership, we have established a system to ensure the successful coordination of research activities across all collaborating organizations. Specifically, the PIs and research managers from NNHSC, NU, and Alliance of Chicago biweekly during the EHR-system build and through project launch. Additionally, the Alliance research manager, project director (from NU), and Quitline manager meet once monthly to address any issues that arise regarding development, study implementation, and evaluation.

Setting

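### The supplementary sample of participants reached at week 28 is written for all three aims, so it drops every short-timeline participant and filters the week-6 and week-14 call outcomes on later contact that they do not need

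*Combined protocol and SAP*

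**What the plan says.** The Data Analysis section treats the three primary outcomes together ("treatment engagement, treatment utilization, smoking cessation) and can be analyzed using logistic regression methods"). The lead analysis is clear: "Analyses will be conducted first using an ITT principle (missing=treatment failures". A second analysis follows: "We will also conduct an adherence sample analysis that includes only participants reached at the 28-week follow-up". The plan expects at least 75% of the sample to be reached. It says that this second analysis gets at effectiveness more directly, but warns that "it is subject to more bias if attrition is large or differential by treatment condition". It therefore adds a study of non-response and inverse-probability weighting on sociodemographic factors, time since the last clinic visit and insurance type. Rates are to be shown for every outcome, and agreement across the three approaches is to count as support for the results.

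Four other places bear on this:

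- **Purpose of Study & Objectives:** Aim 1 is a completed counselling call by week 6. Aim 2 is at least one further call by week 14.
- **Multiple Sites:** Quitline staff will "electronically send the treatment outcomes information to the NNHSC EHR for all participants who complete Quitline counseling sessions". The clinic workflow text adds daily transmission and a separate tracking code for Usual Care.
- **Alternative study timeline (Study Design):** people enrolled from February 2018 are followed "through a final follow-up at week 14".
- **Treatment Outcomes (Measures):** utilization is defined as a further call together with receipt and use of NRT.

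**The concern.** Two things go wrong if the text is followed literally.

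First, a short-timeline participant has no week-28 contact and so cannot enter the sample, however well followed. That exclusion is structural, applies to all three aims, and needs no assumption about behaviour.

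Second, for Aims 1 and 2 the sample is selected on an event that comes after randomisation and after the outcome. Someone who has taken up counselling may be easier, or harder, to reach months later. If that link differs between arms, the comparison among those reached is distorted, although the call outcome did not depend on the interview. Because agreement between approaches is to be read as corroboration, a supplementary result of this kind could lend support that it has not earned, or cast doubt on a sound lead result.

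**Working it through.** **Inputs from the documents.** 265 per arm; two-sided alpha 0.05; Aim 1 rates 10% v 24%; Aim 2 rates 7% v 15%; expected week-28 reach at least 75%. **Not in the documents, so assumed:** reach by arm and by outcome, and the share of participants on the short timeline.

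**1. The plan's own power.** For two proportions with pooled variance under the null, where p̄ is the mean of p1 and p2:

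power = Φ{ [(p2 − p1) − 1.96·√(2p̄(1−p̄)/n)] / √[(p1(1−p1) + p2(1−p2))/n] }

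Aim 2, n = 265: p̄ = 0.11. The null term is 1.96·√(0.1958/265) = 0.0533 and the denominator is √(0.1926/265) = 0.0270. Then (0.08 − 0.0533)/0.0270 = 0.99, and power is 83.9% (stated 84%). Aim 1 gives 99.1% (stated 99%). The plan's figures reproduce.

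**2. Power in the restricted sample, with no bias at all.**

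| Sample | n per arm | Aim 1 | Aim 2 |
|---|---|---|---|
| All randomised | 265 | 99.1% | 83.9% |
| 75% reached, nobody on short timeline | 199 | 96.3% | 72.4% |
| 10% on short timeline, 75% of the rest reached | 265 × 0.9 × 0.75 = 179 | 94.4% | 67.8% |
| 50% on short timeline, 75% of the rest reached | 265 × 0.5 × 0.75 = 99 | 75.1% | 43.7% |

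The last two samples hold 67.5% and 37.5% of those randomised.

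**3. Selection on being reached.** Let r1 and r0 be the probabilities of being reached with and without the outcome. The rate seen among those reached is q = p·r1 / [p·r1 + (1−p)·r0]. The odds in an arm are therefore multiplied by r1/r0. If r1/r0 is the same in both arms, it cancels from the odds ratio.

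True Aim 1 values: odds ratio (0.24/0.76)/(0.10/0.90) = 2.84, risk difference 14.0 points.

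- *Same dependence in both arms*, reach = expit(0.95 + d·engaged), so r0 = 0.721:
  - d = 0.5, r1 = 0.810: q = 26.2% v 11.1%, difference 15.1 points, odds ratio 2.84.
  - d = 1.0, r1 = 0.875: q = 27.7% v 11.9%, difference 15.8 points, odds ratio 2.84.
- *Dependence in Choose to Change only*, Usual Care flat at 75%:

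| Reach in Choose to Change, engaged / not | Aim 1 odds ratio | Risk difference |
|---|---|---|
| 85% / 73% | 3.31 | 16.9 |
| 90% / 70% | 2.84 × 0.90/0.70 = 3.65 | 18.9 |
| 95% / 65% | 4.15 | 21.6 |
| 60% / 80% (reversed) | 2.84 × 0.60/0.80 = 2.13 | 9.1 |

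In the 90%/70% case, overall reach in Choose to Change is 0.24 × 0.90 + 0.76 × 0.70 = 74.8%, against 75% in Usual Care. A comparison of attrition by arm would not show the problem. Under the same pattern the Aim 2 odds ratio goes from 2.35 to 3.01. With no true effect and a 10% rate in both arms, the Aim 1 odds ratio would be 1.29 and the test would reject about 12% of the time instead of 5% (7.6% to 22.3% from 85%/73% to 95%/65%).

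**4. Would the planned weights repair this?** The weighting variables listed for all outcomes are sociodemographic and healthcare characteristics. They can remove selection that runs through those variables, but not selection that depends on engagement itself. For Aims 1 and 2 engagement is the outcome. Where it is known for everyone from call records, the direct remedy is to analyse everyone.

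**The case against.** The strongest reply is that little is at stake. Intention-to-treat comes first, on everyone randomised; the restricted analysis is an addition. The plan itself names the risk of bias, studies non-response, offers weighting, and says to refrain from further comparison if propensity overlap is poor. The planned model is logistic, so when the dependence of reach on engagement is the same in both arms, the estimated odds ratio and the test of no effect are unaffected. Bias in the odds ratio needs dependence that differs by arm, and the documents give no reach rates from which to judge that. All of this stands, and it keeps the point supplementary.

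A second reply concerns data sources. A reader might infer that Quitline records supply Aims 1 and 2 completely for everyone. The documents do not go that far. The transmission statement covers people who complete sessions. The survey section says that many outcome variables are not available from the Quitline for those who do not engage, and the survey itself asks about Quitline treatment. No place says that NRT use, part of utilization as defined under Measures, comes from Quitline records. This limits the argument to completed calls. There it still holds: the absence of a recorded call is the outcome value, and Usual Care has its own tracking code. An NRT component due at week 14 would call for week-14 data, not week-28 contact.

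Neither reply answers the exclusion of short-timeline participants. Measures does give them a week-14 carbon monoxide check, but the rule in Data Analysis does not carry it over.

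**Conclusion.** The point holds for the supplementary analysis as written. Exclusion of all short-timeline participants follows directly from the text; its size does not, because their share is not stated. The loss of precision is certain in direction: Aim 2 power in this sample is 72% at 75% reach, and about 68% to 44% if 10% to 50% are on the short timeline, against 84% in all randomised participants. Bias for Aims 1 and 2 is possible, with size and direction unknown. The Aim 1 odds ratio of 2.84 may be unchanged, raised to 3.65 or lowered to 2.13 under the assumed reach patterns.

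Three stronger readings are not supported:

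- That the restriction necessarily biases Aims 1 and 2. It need not, as the equal-dependence case shows.
- That randomised data are discarded or replaced. The lead analysis keeps everyone.
- That at least a quarter of participants are lost. An expected reach of at least 75% means at most 25% of those who have a week-28 visit. The Retention section does say "we expect at least a 60% participation rate across the four surveys", but that may measure something else, and the two figures should be reconciled. At 60% reach, Aim 2 power in this sample would be 62.6%.

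**What to change.** In the Data Analysis section:

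1. Limit the responder and weighted analyses to Aim 3, defined at each participant's own final visit: week 28, or week 14 on the alternative timeline.
2. State that Aims 1 and 2, as far as they rest on completed calls, are analysed in all randomised participants.
3. Say whether NRT use is part of the Aim 2 outcome. If it is, give its data source, and base any responder analysis of it on week-14 contact.
4. Delete the statement that the responder analysis addresses effectiveness more directly. A name such as follow-up responders would describe the set better than adherence, but that is only terminology.

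The cost is a few sentences of SAP text. No new data are needed for the call outcomes, and there are fewer analyses to run.

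### The weighting offered against attrition mixes a response score with a treatment propensity score, so it corrects only bias that nine listed covariates explain, and its overlap check does not test it

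*Combined protocol and SAP*

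**What the plan says.** The Data Analysis section of the Statistical Analysis Plan sets out three approaches.

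- **ITT, first.** "Analyses will be conducted first using an ITT principle (missing=treatment failures". Measures, Treatment Outcomes, likewise counts anyone who cannot be reached as smoking.
- **Adherence sample.** This analysis "includes only participants reached at the 28-week follow-up", put at 75% or more "of the sample based on our experience". The plan concedes that "it is subject to more bias if attrition is large or differential by treatment condition".
- **Weighting, as the complement to the adherence sample.** Non-response is to be studied with seven sociodemographic and two healthcare variables. "These can be used to create propensity scores that allow for inverse-probability-weighting (IPW) of observed outcomes". The stated goal is balance on confounders of treatment and outcome. Then: "Ideally, the distribution of propensity scores will show large overlap across study conditions". If not, that is evidence that "completers are not comparable on measured confounders across conditions", and further comparison should be avoided. No threshold is given.

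For cessation only, smoking history, race and gender are also explored as predictors of non-response. They are not said to enter the weights. Agreement of all three approaches is to raise confidence, and raw and adjusted rates are to be reported by arm. Retention and Adherence gives another follow-up figure: "we expect at least a 60% participation rate across the four surveys".

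**The concern.** The weighting is introduced because some participants will not be reached, possibly more in one arm. That calls for a model of being reached. The stated goal and the overlap check belong to a different model, one for arm membership among those reached. An analyst could fit either, and the text does not say which.

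The predictor list does not match the stated worry. It includes neither arm nor any arm-by-covariate term. It also leaves out variables that the trial collects and that could plausibly bear on both follow-up and quitting: readiness to quit (a stratification factor), cigarettes per day, Quitline engagement, and smoking status at weeks 6 and 14. Preferred language, another stratification factor, is absent too.

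At stake is the credibility of the attrition analysis for Aim 3. If the weights largely reproduce the adherence-sample result, agreement between those two approaches would be read as support when it carries little information about attrition.

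**Working it through.** **1. The plan's own figure.** None is given for the weighted analysis. The nearest is 80% power for Aim 3 (2% v 7%, 265 per arm, two-sided 0.05). With the pooled test: null SE = √(2 × 0.045 × 0.955/265) = 0.01801; alternative SE = √((0.02 × 0.98 + 0.07 × 0.93)/265) = 0.01788; power = Φ((0.05 − 1.96 × 0.01801)/0.01788) = Φ(0.822) = 79.5%. This reproduces. I take 2% and 7% as the truth: difference 5.0 points, odds ratio (0.07/0.93)/(0.02/0.98) = 3.69.

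**2. Which score the text describes.**

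| Feature | Response score | Treatment score among completers | Plan |
|---|---|---|---|
| Reason for it | Attrition | Imbalance between arms | Attrition |
| Modelled outcome | Reached or not | Arm | Not stated |
| Role of arm | Predictor | Outcome of the model | Not mentioned |
| Goal | Represent all randomised | Balance the arms | Balance confounders |
| Check | Response probabilities within arm not near zero | Overlap across arms | Overlap across arms |

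The reason comes from the first column; the goal and the check come from the second.

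**3. What weights on listed variables can do.** Assumptions, not from the documents: one listed binary covariate X (risk ratio 1.5 for abstinence), one unlisted binary covariate U (risk ratio 3), each with 50% prevalence, 75% reached overall, logistic response. Averaged over U, rates for X = 0 and 1 are 1.6% and 2.4% (Usual Care), 5.6% and 8.4% (Choose to Change). Averaged over X, rates for U = 0 and 1 are 1.0% and 3.0%, 3.5% and 10.5%.

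- *Response depends on X only* (0.840, 0.660). Unweighted: Usual Care (0.840 × 1.6 + 0.660 × 2.4)/1.5 = 1.95%; Choose to Change (0.840 × 5.6 + 0.660 × 8.4)/1.5 = 6.83%; difference 4.88. Weights on X restore 5.00.
- *Response depends on arm only* (about 82% v 68%). No bias, with or without arm in the weights.
- *Response depends on X differently by arm* (Usual Care 0.772, 0.902; Choose to Change 0.772, 0.554). Unweighted 4.74. Weights on X alone give 4.77 (odds ratio 3.50); weights on arm and X together give 5.00.
- *Response depends on U, equally in both arms* (0.660, 0.840). Usual Care (0.660 × 1.0 + 0.840 × 3.0)/1.5 = 2.12%; Choose to Change (0.660 × 3.5 + 0.840 × 10.5)/1.5 = 7.42%. Weights on X leave the difference at 5.30; the odds ratio is 3.70.
- *Response depends on U in opposite directions by arm* (Usual Care 0.772, 0.554; Choose to Change 0.772, 0.902). Usual Care (0.772 × 1.0 + 0.554 × 3.0)/1.326 = 1.84%; Choose to Change (0.772 × 3.5 + 0.902 × 10.5)/1.674 = 7.27%. Weights on X leave 5.44 and odds ratio 4.19. X is split 50/50 among completers in both arms, so the overlap check passes.

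**4. Size with the plan's rates.** From the Power section: engagement 10% and 24%; abstinence 3% and 10% at the earlier visit, 2% and 7% at the later one. Its text labels these visits 12 and 26 weeks; I use them for weeks 14 and 28. Assumptions: engagement triples week-14 abstinence; a share q of week-28 quitters (60% to 90%) were already abstinent at week 14; given that status, engagement has no further effect on week-28 abstinence; response has the same log-odds b for engagement and for week-14 abstinence; 70% are reached; listed variables are unrelated to all of these.

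Worked case, b = 1.0, q = 0.9:

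- Week-14 abstinence in non-engaged and engaged: Usual Care 0.03/1.2 = 2.5% and 7.5%; Choose to Change 0.10/1.48 = 6.76% and 20.27%.
- Week-28 abstinence given week-14 abstinence: 0.9 × 0.02/0.03 = 60%; 0.9 × 0.07/0.10 = 63%. Otherwise: 0.1 × 0.02/0.97 = 0.206%; 0.1 × 0.07/0.90 = 0.778%.
- Response with neither, one or both predictors (intercept 0.663, solved for 70%): 0.660, 0.841, 0.935. By arm: 68.3% and 71.7%.
- Share of completers abstinent at week 14: 3.80% and 12.36%.
- Completer rates: 0.0380 × 60 + 0.9620 × 0.206 = 2.48%; 0.1236 × 63 + 0.8764 × 0.778 = 8.47%. Difference 5.99; odds ratio 3.64.

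| b | q | Usual Care | Choose to Change | Difference | Odds ratio |
|---|---|---|---|---|---|
| 0.5 | 0.6 | 2.18% | 7.56% | 5.4 | 3.67 |
| 0.5 | 0.9 | 2.27% | 7.90% | 5.6 | 3.69 |
| 1.0 | 0.6 | 2.31% | 7.92% | 5.6 | 3.63 |
| 1.0 | 0.9 | 2.48% | 8.47% | 6.0 | 3.64 |

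Solving the intercept for 75% reached instead gives 5.3 to 5.8 points, and for 60% gives 5.5 to 6.4. If b is 0.5 in Usual Care and 1.0 in Choose to Change (q = 0.9, 70% reached), the odds ratio is 3.94.

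**The case against.** Several points on the other side stand.

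- **Scope.** This is the third of three approaches, worded permissively. The primary cessation analysis has no missing outcomes to weight. A reader might infer that the weighting is the trial's main protection for Aim 3, or that the stop rule could cancel the randomised comparison. The documents support neither. The rule speaks of completers, so in context it stops only the adherence-sample and weighted comparisons.
- **The rule is not invalid in itself.** For a score of arm membership among completers, overlap across arms is a standard check, and arm cannot be a predictor because it is the modelled outcome. But such a score does not address who was reached, which is why the weighting was introduced.
- **The weights do some good.** It would be too strong to say that they do not correct attrition bias. They remove it fully when response depends only on the listed variables, and leaving out arm alone need not cause bias.
- **Drop-out predictors are unknown.** The documents report none, so it cannot be said that the main ones are missing. Smoking history is explored for non-response, though not placed in the weights.
- **The size is assumed.** In step 4 the listed variables were made unrelated to response, so their failure to help is built in. On the odds-ratio scale of the planned logistic regression the same mechanism does little: 3.63 to 3.69 against 3.69.

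After these concessions the mixed specification remains, as does a check that can pass while bias remains.

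**Conclusion.** The point holds for the secondary weighted completer analysis. The section does not settle which score is modelled, its predictor list omits arm and relevant collected variables, and its only diagnostic does not test a response model.

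Under the step 4 assumptions at 70% reached, completer rates are 2.18% to 2.48% against 2%, and 7.56% to 8.47% against 7%. The difference is 5.4 to 6.0 points against 5.0, in favour of the intervention, and the listed weights leave it there. The consequence therefore falls on the adjusted rates and the risk difference. The odds ratio is materially biased only if response predictors act differently by arm: 3.94 in the case in step 4, and 3.50 or 4.19 in the two such cases in step 3. None of these figures predicts the trial's result, because the documents do not say what drives response. The missing-as-failure ITT analysis is not affected.

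**What to change.** Amend the Data Analysis text as follows.

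- Define the score as the probability of being reached at the participant's biochemically verified endpoint: week 28, or week 14 on the short timeline. Participants on the short timeline have no week-28 visit by design and must not be modelled as week-28 non-responders.
- Fit it separately within each arm, or with arm and arm-by-covariate terms.
- Add to the listed variables the stratification factors not already there (readiness and language), baseline cigarettes per day, Quitline engagement, and smoking status at waves before the endpoint. Post-randomisation variables belong in the response model only, not as covariates in the comparison of arms.
- Report response probabilities and weight distributions within each arm, with a stated rule for very small probabilities. Let this replace the stop rule based on overlap across conditions.

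The cost is SAP wording and slightly more analysis work. The variables are already collected. The drawback is somewhat more variable weights.
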